7. RESEARCH QUESTIONS AND OBJECTIVE(S)

Following the initiation of any ARV regimen containing CAB and/or RPV LA among PLWH, the study will aim to assess usage patterns, durability, discontinuation, and virologic outcomes.

The specific objectives are to:

- 1. Describe CAB and/or RPV LA containing regimens usage patterns
 - Descriptive analysis of study population by baseline demographic and clinical characteristics
 - Monitor for use of oral lead-in
 - The potential regimen combinations are listed below (Note that CAB+RPV LA is the only approved regimen)
 - a. CAB+RPV LA regimen only
 - b. CAB LA monotherapy
 - c. CAB LA use in combination with ARVs other than RPV LA
 - d. RPV LA monotherapy
 - e. RPV LA use in combination with ARVs other than CAB LA
 - f. CAB LA+RPV LA+other ARVs
 - g. Combined group b-f
- 2. Assess adherence, durability and discontinuation for persons starting CAB+RPV LA regimen;
 - Proportion of individuals discontinuing the regimens of interest will be assessed.
 - Reasons for discontinuation will be assessed.
 - Non-adherence to the dosing schedule will be assessed by:
 - a. Estimating the number of individuals that missed one or more consecutive injections without taking daily oral bridging therapy or any other oral ARV regimen while not on CAB+RPV LA containing regimens and mean and median number of injections missed during a 12-month period
 - b. Estimating the number of individuals who received the injections seven or more days later than their scheduled injection visit and median duration of delayed injections
 - c. Estimating the number of individuals who missed one or more consecutive injections without taking daily oral bridging therapy or those who received the injections seven or more days later than their scheduled injection visit (Combined group a OR b) and describe patient characteristics for the individuals that are nonadherent.
 - Number of individuals with incorrect route of administration will be described.

- 3. Assess the clinical effectiveness (i.e. proportion of individuals experiencing virologic failure) among PLWH who initiate CAB+RPV LA regimen
 - a. Estimate the proportion of individuals with virologic failure, during the first 6 months after initiation of CAB+RPV LA
 - b. Estimate the proportion of individuals with virologic failure, at 6, 12 and 24 months after initiation of CAB+RPV LA
 - c. Stratified analyses for 3a and 3b will be conducted for VL at regimen initiation (<50 copies/mL and ≥50 copies/mL).

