8.2. Study Population and Setting

Study Population:

The study population will include PLWH over the age of 18 years, from EuroSIDA clinical sites who are new users of CAB and/or RPV LA containing regimens over a period of 5 years. Persons will be eligible for inclusion from the date of starting the treatment regimens after approval and commercial availability of the regimens. Only the first exposure to CAB and/or RPV LA containing regimens will be included in the primary analyses.

The potential regimen combinations are listed below (Note that CAB+RPV LA is the only approved regimen):

- a. CAB+RPV LA regimen only
- b. CAB LA monotherapy
- c. CAB LA use in combination with ARVs other than RPV LA
- d. RPV LA monotherapy
- e. RPV LA use in combination with ARVs other than CAB LA
- f. CAB LA+RPV LA+other ARVs
- g. Combined group b-f

EuroSIDA Cohort description:

The EuroSIDA study was initiated in 1994 and is a prospective observational cohort study of more than 22,000 individuals followed in over 100 hospitals in 34 European countries, and Israel and Argentina. The main objective of the study is to assess the impact of ARV drugs on the outcome of the general population of PLWH living in Europe.

In EuroSIDA, annual data collection is performed directly from clinics on individuals using comprehensive standardized clinical record forms via REDCap or electronic data transfer using the HICDEP format that includes information on outcomes and covariates [2]; further information is available at https://www.hicdep.org/. For each person, the date of starting and stopping each ARV drug is recorded. ATC codes for all ARVs and most non ARVs are collected. Dates of diagnosis of all AIDS defining diseases are recorded, using the 1993 clinical definition of AIDS from the Centers for Disease Control and Prevention. All EuroSIDA data undergo extensive data checks, queries and central clinical event validation to ensure a high quality and completeness of data.

Table 1. EuroSIDA currently contributing countries and geographical regions

Southern	Central Western	Northern Europe	Central Eastern	Eastern
Europe	Europe		Europe	Europe
Spain	France	United Kingdom	Poland	Estonia
Portugal	Belgium	Ireland	Czech Republic	Lithuania
Italy	Luxembourg	Netherlands	Bosnia-Herzegovina	Belarus
Greece	Switzerland	Denmark	Hungary	Ukraine
	Austria	Sweden	Romania	Russia
	Germany	Norway	Serbia	Georgia
		Finland	Slovenia	
		Iceland	Croatia	
*Israel			Albania	
*Argentina			North Macedonia	

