ANNEX 1. CASE REPORT FORM

CRF completed by: text field

CRF completed date: Year/month/day

(These two items should be included for each follow up injection and hepatotoxicity form)

Data entry instructions

Standard text reg. comma vs. full stop, test not performed, unknown dates

Link to document about data entry, contact for questions etc.

Patient ID: xxx-xxxx

Date of birth: Year/month/day

HIV subtype

Has an HIV subtype test been performed prior to initiation of long-acting antiretroviral therapy yes/no

(If yes)

Date of latest HIV subtype test prior to initiation of long-acting antiretroviral therapy Year/month/day

Subtype drop down menu with subtypes

Oral lead-in antiretroviral therapy

Drug 1 (drop down menu)

1) Cabotegravir

2) Rilpivirine

Start date Year/month/day

Vii V Healthcare Com

CONFIDENTIAL

eTrack Project Number: 215161

Stop date

Year/month/day

Was oral lead-in antiretroviral therapy stopped because the patient has initiated long-acting antiretroviral therapy

Yes/no

If yes, Treatment section below will open

If no, following will open

Reason for discontinuation protocol

Drop down menu with all reasons listed in table 2 in the

Drug 2 etc

(This section of the form refers to the first LAI)

After the first injection with long-acting antiretroviral therapy (LAI), the CRF will capture information about the following scenario's as set out below;

- 1) The patient receives LAI as planned
- 2) The planned LAI is not given, and the patient **starts bridging therapy**. After end of bridging therapy there are three possibilities:
 - a. LAI is resumed in which case we want to know date of injection, dosage etc
 - A decision to stop LAI has been made in which case we want to know why LAI was stopped
 - c. Switched to a different ART regimen
- 3) The planned LAI is not given, and the patient **does not start bridging therapy**. We want to know if the patient later restarts LAI.
 - a. LAI is resumed in which case we want to know date of injection, dosage etc
 - b. A decision to stop LAI has been made in which case we want to know why LAI was stopped
 - c. Switched to a different ART regimen

The CRF will only capture the first exposure to LAI. The second injection for the two-month schedule is given one month after the first injection and hence we will allow three months after the first injection to see if the regimen was resumed (≤2 months) or re-initiated (>2 months). In

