case of resumption of LAI after missed second injection in two months or less, we will still consider it first exposure.

Similarly, the third injection (and injections thereafter) for the two-month schedule is given two months after the second injection and hence we will allow four months after the second injection to see if the regimen was resumed (≤3 months) or re-initiated (>3 months). In case of resumption of LAI after missed third injection in three months or less, we still consider it first exposure.

Treatment with long-acting antiretroviral therapy

Which long-acting antiretroviral drugs have been initiated? (drop down menu)

1) long acting cabotegravir + long acting rilpivirine

2) long acting cabotegravir without rilpivirine

3) long acting rilpivirine without cabotegravir

Dosage: 400/600 mg (CAB) / 600/900 mg (RPV) (drop down

menu)

Date of first injection: Year/month/day

Intended dosing schedule of long-acting antiretroviral therapy Monthly/Every 2 Month

HIV resistance testing (only pops up for the first injection and if CAB + RPV has been selected)

Has a HIV resistance test been performed prior to initiation of long-acting cabotegravir + rilpivirine yes/no

If yes

Date of latest most recent resistance test prior to initiation of long-acting antiretroviral therapy Year/month/day

Method used drop down menu

Please upload a copy of the resistance test report (result will be based on central review)

(After completion of date of first injection, a new section will open for second injection with target date one month after the first injection. All the questions below refer to subsequent injections after the first)

Has the patient received the next planned injection with long-acting antiretroviral drugs yes/no

If yes, Which long-acting antiretroviral drugs were given? (drop down menu)

1) long acting cabotegravir + long acting rilpivirine

2) long acting cabotegravir without rilpivirine

3) long acting rilpivirine without cabotegravir

Dosage: 400/600 mg (CAB) / 600/900 mg (RPV) (drop down

menu)

Date of injection: Year/month/day

Intended dosing schedule of long-acting antiretroviral therapy Monthly/Every 2 Month

(if the patient switches from monthly to two-monthly injections or vice versa, a new question pops up)

Reason for switching to monthly (or 2 monthly) injection schedule (drop down menu)

- 1. Convenience
- 2. To reduce cost
- 3. To reduce side effects
- 4. Personal reasons
- 5. Other (+ text field)

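### If the first-exposure limit governs, un-bridged returns over about a month late on the two-month schedule drop out of objective 2, capping missed-injection counts and delays; other sections imply they are kept

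*Protocol*

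**What the plan says.** Objective 2 in Section 7 asks how many people miss one or more consecutive injections without oral cover, with the "mean and median number of injections missed during a 12-month period" (2a). It also asks how many are seven or more days late, with the "median duration of delayed injections" (2b), and for the two groups combined (2c).

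Annex 1 sets the scope of the form: "The CRF will only capture the first exposure to LAI". For the second injection on the two-month schedule, "we will allow three months after the first injection to see if the regimen was resumed (≤2 months) or re-initiated (>2 months"). For the third and later ones, "we will allow four months after the second injection to see if the regimen was resumed (≤3 months) or re-initiated (>3 months"). A return inside the shorter limit stays in the exposure: "In case of resumption of LAI after missed third injection in three months or less, we still consider it first exposure". Section 8.2 adds: "Only the first exposure to CAB and/or RPV LA containing regimens will be included in the primary analyses".

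Other text points the other way or defines things differently:
- Annex 1, scenario 3 (planned injection not given, no bridging): "We want to know if the patient later restarts LAI". The matching branch of the form asks for the restart date and gives no time limit.
- Annex 1 also says that every injection up to 24 months plus six weeks after initiation is collected. Section 8.3.1 says that all planned and actual injection dates are collected.
- Section 8.3.2 dates an un-bridged discontinuation at the end of the 7-day window after the due date.
- Sections 8.3.2 and 8.6 (Aim 2) give the median delay in persons using bridging therapy. Section 7 has no such limit.

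**The concern.** Objective 2 is meant to measure how far people depart from the injection schedule. A rule that ends the observed exposure about one month after a missed due date removes the larger departures from that measurement. Within one un-bridged gap followed by a return, no more than one injection can be counted as missed, and no delay can exceed about a month, whatever happens in practice.

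Section 6.2 gives the impact of non-adherence on virologic failure and resistance as a reason for the study. Missed and delayed doses are explanatory variables in Aims 3 and 4, and non-adherence is one of the measures of routine risk minimisation in Aim 5. If the rule governs the form, the later dates are not collected, and no analysis plan can restore them. If they are collected but Section 8.2 excludes them, the adherence summaries are still cut.

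**Working it through.** **Step 1. Where the cut-off falls.** The example in Section 8.3.2 has injections due on 1 June, 1 July and 1 September; the next is due on 1 November. Counting Annex 1's limits from the previous injection gives:

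| Injection | Due | Limit for resumed | Days after due | Look window ends | Days after due |
|---|---|---|---|---|---|
| Second | 1 July | 1 June + 2 months = 1 Aug | 31 | 1 June + 3 months = 1 Sept | 62 |
| Third | 1 Sept | 1 July + 3 months = 1 Oct | 30 | 1 July + 4 months = 1 Nov | 61 |

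Both limits are the due date plus one month (28 to 31 days, depending on the calendar). Counting from the missed due date does not work. For the third injection the limit would be 1 September + 3 months = 1 December, after the look window has closed on 1 November.

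**Step 2. A whole skipped injection.**
- Second skipped, return 1 September: 3 months after the first injection, against a limit of 2.
- Third skipped, return 1 November: 4 months after the second injection, against a limit of 3.
- Returning 7 days early (25 August or 25 October) is still past 1 August or 1 October.

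Such a return therefore always falls outside first exposure. The look window reaches exactly to the next due date, so a return on that day can be seen and classed as re-initiated. A return on 2–8 November, inside the allowed +7 days, falls after the window. So does a return on 1 January after two consecutive misses.

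**Step 3. Overlap with the discontinuation date.** Section 8.3.2 discontinues an un-bridged person at due + 7 days (8 July, 8 September). Annex 1 keeps the same person in first exposure to 1 August or 1 October. For 24 days (9 July–1 August) or 23 days (9 September–1 October) the person is both discontinued and still in first exposure.

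**Step 4. Effect on the median delay.** The protocol gives no delay distribution, so this is an assumption. Let the delay among late injections be 7 days plus an exponential excess with mean m, and let c be the cut (28 or 31 days).
- Uncut median = 7 + m ln 2.
- Share dropped = exp(−(c − 7)/m).
- Cut median = 7 − m ln(1 − F/2), with F = 1 − share dropped.

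Example, m = 30 and c = 31: share dropped = exp(−24/30) = 0.449; F = 0.551; cut median = 7 − 30 ln(0.7245) = 16.7 days; uncut median = 7 + 30 × 0.693 = 27.8 days.

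| Mean excess m (days) | Uncut median | Cut median (c = 28 to 31) | Late returns dropped |
|---|---|---|---|
| 7 | 11.9 | 11.5–11.6 | 3–5% |
| 14 | 16.7 | 13.9–14.4 | 18–22% |
| 30 | 27.8 | 15.7–16.7 | 45–50% |
| 60 | 48.6 | 16.6–17.8 | 67–71% |
| 90 | 69.4 | 16.9–18.2 | 77–79% |

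From a mean excess of 30 days upward, the cut median hardly responds to the true one. These figures concern un-bridged delays on the two-month schedule, with the median taken as Section 7 words it.

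**The case against.** The strongest reply is that the form does collect later returns. Scenario 3, the un-bounded restart question, the line on all injections to 24 months plus six weeks, and Section 8.3.1 all say so, and the look window exists to tell resumed from re-initiated. This stands to the extent that data loss is one reading of conflicting text. A reader might infer that nobody who skips an injection and returns can be seen at all. The documents do not support that: a return on the next due date falls on the last day of the look window, and the miss is recorded, so the count of people with at least one miss need not suffer. The reply does not remove the conflict with the sentence limiting the form to first exposure. Nor does it touch Section 8.2, under which later exposure stays out of the primary analyses even when recorded.

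Second, Sections 8.3.2 and 8.6 report the median delay in bridging users, and the calculation above does not describe that figure. This is correct. It applies to the Section 7 wording, and the difference itself needs settling.

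Third, long un-bridged gaps are not hidden altogether. They are tabulated as discontinuations with reasons and followed for up to 48 months, and intent-to-treat sensitivity analyses assess virologic outcomes regardless of discontinuation. This also stands, so it goes too far to say that Aim 5 would necessarily reassure wrongly. It does not supply the number of injections missed or the length of delay.

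Fourth, restricting effectiveness analyses to first exposure is a normal new-user choice. That is accepted, and the fix leaves it alone.

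**Conclusion.** The point holds conditionally. If the first-exposure limit in Annex 1 and Section 8.2 governs objective 2, a whole skipped two-monthly injection followed by an un-bridged return always falls outside the data used. The number of injections missed (2a) and the length of un-bridged delays (2b as worded in Section 7) are then capped and biased downward. A reader might infer that the rule fixes the reported median. It only caps the delays, which can lie anywhere from 7 to about 31 days.

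The size is unknown: negligible if late returns are mostly within two weeks of the due date, large if they commonly run to a month or more.

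This rests on four assumptions: the exponential form; counting the limits from the previous injection, the only coherent reading; applying them to un-bridged gaps, since the cut-off sentences do not mention bridging; and taking the primary analyses in Section 8.2 to include objective 2. The cut-offs are stated for the two-month schedule only, so the effect on figures pooled over both schedules cannot be given.

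Independently of size, three conflicts need reconciling: first exposure only against all injections to 24 months plus six weeks; discontinuation at due + 7 days against first exposure to due + one month; and the median delay in all late injections against bridging users only.

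**What to change.** 1. Reconcile Annex 1 with Sections 8.2, 8.3.1 and 8.3.2 on which injections are recorded and when an un-bridged person leaves the exposure. This review does not say which limit is right.
2. State in Annex 1 that all injection dates after any return are recorded up to the existing limit of 24 months plus six weeks, and keep resumed or re-initiated only as a flag.
3. State in Section 8.6 (Aim 2) that the number of scheduled injections missed and the delay, from due date to next actual injection, are computed for objectives 2a–2c over all returns, with people who have not returned reported separately.
4. Use one population for the median delay in Sections 7, 8.3.2 and 8.6.
5. Keep the first-exposure restriction for the effectiveness analyses.

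The cost is a few extra injection rows for people who return late, some sentences of protocol text, and adherence figures that may look less favourable. The form already has the fields.

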^{*}non-European countries

Data Collection:

Following the approval and commercial availability of CAB+RPV LA, the study will collect prospective data on individuals initiating CAB and/or RPV LA containing regimens, over the course of 5 years. The EuroSIDA coordinating center will receive data from the clinical sites per the protocols established for data collection.

An additional data collection form will be used to enhance the routinely collected data from clinical sites. Dates of treatment, documented history of resistance at regimen initiation, resistance and HIV subtype data at virologic failure and after discontinuation and switching to another ARV regimen will be collected via the enhanced data collection using study specific additional CRFs. The additional CRF will collect baseline data at regimen initiation, 6 months, 12 months & 24 months for all individuals on the CAB and/or RPV LA containing regimen of interest and at 12 months, 24 months, 36 months & 48 months for those who discontinue the regimen and switch to other ARV regimens.

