Descriptive analyses will compare those with and without virologic failure to assess any differences in baseline characteristics of the two groups. Detailed analysis of additional risk factors will be limited to persons with 6, 12 or 24 months of follow-up. Multivariable logistic regression models will investigate the factors associated with virologic failure at 6 months, 12 months and 24 months after CAB+RPV LA initiation. Potential explanatory variables are listed above. We will also investigate the impact of missed doses and use of oral bridging therapy by using the data collected via the CRF. Multivariate analyses will be performed when > 30 persons on CAB+RPV LA have virologic failure and analyses will be limited to persons with > 6-, 12- or 24-months follow-up. The model building strategy will follow EuroSIDA protocol and include variables significant in univariate analyses as well as *a priori* pre-specified variables of interest. Primary analysis for clinical effectiveness will include individuals on CAB+RPV LA, with VL of <50/copies/mL at regimen initiation. In addition, all the analyses will be conducted separately for individuals on CAB+RPV LA with VL of ≥50 copies/mL at regimen initiation.

Our primary analyses of virologic outcomes will censor follow-up at discontinuation of CAB+RPV LA, last visit or death, whichever occurs first, an on-treatment approach to analysis. Sensitivity analyses will use an intent to treat approach and virologic outcomes will be assessed regardless of regimen discontinuation.

We will perform additional sensitivity analysis limited to those who start CAB+RPV LA with resistance data available, to confirm no present or past evidence of viral resistance to, and no prior virological failure with agents of the NNRTI and INSTI class.

AIM 4. Monitor for resistance and next treatment response among individuals who switched off CAB+RPV LA regimen

Monitoring for resistance

Since this is a non-interventional study aiming to capture individual care in real world setting, the study will not mandate resistance testing following discontinuation of the regimen of interest. Health care providers following the local treatment guidelines decide

what laboratory and resistance tests are to be conducted. Data thus generated will be captured and analyzed by the study team.

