Descriptive statistics will describe and compare the ARV regimen individuals are switched to after discontinuation of CAB+RPV LA regimen. As resistance testing will not be common, we will describe the characteristics of those with and without resistance testing at virologic failure and again at virologic failure during the 12, 24, 36 and 48 months after switching regimens and use logistic regression to identify factors associated with resistance testing. Where more than 1 resistance test is available during the 12, 24, 36 and 48 months after stopping CAB+RPV LA regimen, cumulative resistance data will be collected and reported.

Study will monitor for resistance at virologic failure and again at virologic failure during the 12, 24, 36 and 48 months following the switch, where resistance data are available. Resistance patterns in those with resistance testing will be summarized. Depending on the number of resistance tests performed and amount of resistance detected, logistic regression will be used to identify factors associated with resistance to CAB+RPV LA. Potential explanatory variables are listed above including missed and delayed doses and use of bridging therapy.

Next treatment response

The study will describe virologic success at 12, 24, 36 and 48 months after discontinuation of CAB+RPV LA regimen, using virologic failure definition as described above. Given that this study involves persons in routine clinical care, and who may not attend clinic appointments every 12 months, a window of 12 weeks around the date in question will be used for virologic testing data. Thus, the proportion with virologic success at 12, 24, 36 and 48 months \pm 6 weeks will be used; and if none is available, the first measurement after 6 or 12 months will be used.

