Descriptive analyses will compare those with and without virologic failure to assess any differences in baseline characteristics of the two groups. Multivariable logistic regression models will investigate the factors associated with virologic failure at 6 months, 12 months and 24 months after regimen initiation. We will also investigate the impact of missed doses and use of oral bridging therapy by using the data collected via the CRF Multivariate analyses will be performed when > 30 persons on the regimen of interest have virologic failure and analyses will be limited to persons with > 6-, 12- or 24-months follow-up.

Depending on the numbers, additional analysis stratifying by VL at regimen initiation (<50 copies/mL and ≥50 copies/mL) will be conducted. We will perform additional sensitivity analysis limited to those who start one of the other regimens with resistance data available, to confirm no present or past evidence of viral resistance to, and no prior virological failure with agents of the NNRTI and INSTI class.

Completeness of data

Not all variables within EuroSIDA are complete for all persons; missing data is rarely missing at random from observational cohort studies. Data may be categorized, including a category for missing, persons may be completely excluded with missing data, or imputation can be used. None of these approaches is likely to be unbiased, but with a small number of primary endpoints anticipated, excluding those with missing data would not be a reasonable approach to analysis.

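### The baseline resistance item on the CRF asks only for the latest test, and only for CAB + RPV starters, so it cannot support the two sensitivity analyses on past resistance

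*Protocol*

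**What the plan says.** Annex 1 first asks whether a resistance test was done before long-acting CAB + RPV was started. If so, it asks for "Date of latest most recent resistance test prior to initiation of long-acting antiretroviral therapy", the method, and an upload of that report for central review. A note on the form says that the item "only pops up for the first injection and if CAB + RPV has been selected".

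The body of the protocol is wider:

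- Section 8.2 (Data Collection) says the additional CRFs will supply "documented history of resistance at regimen initiation, resistance and HIV subtype data at virologic failure".
- Section 8.3.1 places resistance testing before initiation on the separate CRF for regimens with CAB LA, RPV LA or both.
- Section 8.3.3 lists previous drug resistance as a baseline variable, where available.
- Section 8.6, Aim 3, plans a sensitivity analysis in CAB+RPV LA starters who have resistance data, "to confirm no present or past evidence of viral resistance to, and no prior virological failure with agents of the NNRTI and INSTI class".
- Section 8.6, Aim 5, plans the same analysis "limited to those who start one of the other regimens with resistance data available".

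After discontinuation the rule is different. The Annex 1 form used then asks sites to enter every resistance test, and under Aim 4, where there is more than one test, "cumulative resistance data will be collected and reported".

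**The concern.** Absence of past resistance is a statement about the whole record, and the latest report covers only part of it. An earlier report may show an NNRTI or INSTI mutation that the latest one does not, because the latest test covered other drug classes or no longer detected the mutation. A site that completes the form correctly in such a case sends in only the later report.

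For regimens that contain only one of the two long-acting drugs, the form asks nothing about baseline resistance, yet Aim 5 promises an analysis that depends on it.

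Three things are at stake: whether the two sensitivity analyses can do what they state, how complete the resistance-history covariate is, and how resistance found at failure can be interpreted. Aim 4 may model that resistance against missed and delayed doses. Without the earlier reports, a mutation seen at failure cannot be checked against what was already documented before the first injection. An analysis plan cannot repair this later, because it cannot recover reports that were never requested.

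**Working it through.** The plan gives no figure on this point, so the check sets the CRF against the text that relies on it.

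**Step 1: which regimen groups see the item.** The form's drug menu has three options: both long-acting drugs ("long acting cabotegravir + long acting rilpivirine"), CAB LA without RPV, and RPV LA without CAB. The groups are those of Sections 7 and 8.2.

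| Group | Regimen | CRF option | Item shown? | Baseline resistance collected |
|---|---|---|---|---|
| a | CAB LA and RPV LA only | 1 | yes | latest test only |
| b | CAB LA alone | 2 | no | none |
| c | CAB LA with ARVs other than RPV LA | 2 | no | none |
| d | RPV LA alone | 3 | no | none |
| e | RPV LA with ARVs other than CAB LA | 3 | no | none |
| f | both LA drugs with other ARVs | 1 | yes | latest test only |

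Groups b to f are the off-label regimen combinations. Four of these five (b, c, d, e) never see the item. Group f does.

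**Step 2: is there another route to the test results?** Section 8.2 assigns resistance history to the additional CRFs. Table 2 in Section 8.3, which lists the routinely collected variables, includes HIV-RNA, CD4 count and hepatitis markers but no resistance result. The protocol therefore names no other source for earlier reports.

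**Step 3: promise against collection.**

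| Statement | Data it needs | What the CRF gives |
|---|---|---|
| 8.2: history of resistance at initiation | all earlier reports | one report, groups a and f |
| 8.3.1: testing before initiation, CAB and/or RPV LA | groups a to f | groups a and f |
| 8.6 Aim 3: no present or past resistance, CAB+RPV LA | all earlier reports, group a | one report |
| 8.6 Aim 5: the same, other regimens | all earlier reports, groups b to f | one report for f, none for b to e |

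**Step 4: what does not depend on the item.** Section 8.3.2 restricts the primary effectiveness analysis to VL <50 copies/mL at initiation, with no resistance criterion, so those estimates do not change. The other half of the sensitivity criterion, no prior virological failure on the two classes, does not use this item either.

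**The case against.** The best defence is that the form is not the only information on each person.

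- HIV-RNA, ARV start and stop dates, and stop reasons are collected routinely. Table 3 has codes for virological failure (1.1) and for resistance based on a test result (1.5). Someone whose earlier resistance came with recorded failure on an NNRTI or INSTI could be excluded by the prior-failure criterion.
- An uploaded report may itself list earlier results. Central review need not treat a single wild-type or incomplete report as clean, and classification rules may be in the SAP.
- Section 8.8 already says that testing is infrequent and selective, and that retrospective collection through extra CRFs may lower data quality.

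Part of this stands. The prior-failure route will catch some carriers, and the protocol does not state that one clean latest report makes a person resistance-free. But nothing requires a report to include earlier results, a stop code is not a genotype, and central review can read only what is uploaded. Section 8.8 acknowledges sparse testing. It does not acknowledge that earlier tests, and all tests in groups b to e, are not requested.

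A reader might infer more than the documents support:

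- **That no off-label regimen has baseline data.** Group f falls under the first menu option and does.
- **That failure in the sensitivity set is overstated.** The protocol has no data on how many carriers would remain or how often they fail.
- **That older resistance will be reported as emerging on treatment.** Section 6.2 mentions emergence as a motive, but Section 8.6 defines no emergent-resistance endpoint. The supported statement is that the two could not be told apart where an earlier report was not collected.

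**Conclusion.** The point holds as a contradiction between the CRF and the body of the protocol. Followed as written, Annex 1 cannot confirm absence of past NNRTI or INSTI resistance. For groups a and f it requests one report where the history is promised. For groups b to e it requests nothing, so the Aim 5 sensitivity analysis has no CRF resistance data in four of the five off-label groups.

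The consequences are limited to the two sensitivity analyses, the resistance-history covariate and the interpretation of resistance at failure. The primary effectiveness estimates are untouched. No percentage can be attached: the protocol gives neither the number of tests per person nor the frequency of mutations found only on an earlier report. The conclusion assumes that Table 2 and the additional CRFs are the full set of sources, as the protocol presents them. It should be corrected before data collection, but it does not threaten the main results.

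**What to change.** 1. Replace the latest-test item with a request for all available resistance tests before the first injection (Test 1, Test 2, and so on, each with date, method and report), in the format of the post-discontinuation form.
2. Show the item for all three long-acting options.
3. Classify baseline resistance, and membership of both sensitivity sets, by central review of the cumulative pre-initiation record.
4. When resistance at failure is reported, state for each person whether it was present, absent or unknown in that record. Unknown covers no baseline test and a drug class not tested, so that a missing test is not read as absence.

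If the form is to stay as it is, reword Section 8.2 and Aims 3 and 5 of Section 8.6 to what one latest test can show, limit Section 8.3.1 to the regimens for which the item opens, and drop the Aim 5 resistance analysis for groups b to e.

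The cost is one reworded item and one removed display condition. Sites with several old reports upload more than one file, and central review reads them. Old reports will be incomplete in some clinics, as Section 8.8 warns for retrospective collection; the unknown category makes that visible.
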